1.0 Objectives/Specific Aims

Primary Aim: Evaluate the feasibility and acceptability of a multi-component intervention for sexual function.

Hypothesis: At least 80% of randomized participants will complete the study without differential withdraws from the VVA control group.

Exploratory Aims:

Aim 2: Determine which measure (FSFI, ITS or PROMIS SexF) should be the primary outcome for this multi-component intervention for a larger, well powered randomized trial.

Aim 3: Determine the effect size to be able to adequately power a larger randomized trial.

This study is related to an NCI Moonshot priority (F) to minimize the debilitating side effects of cancer treatment. Completion of these aims will provide a critical foundation for NCI Cancer Prevention and Control Clinical Trials Grant Program R01 submission to implement a phase II or III randomized trial to implement in the NCORP network.

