4.0 Methods

4.1 Design

This will be a randomized two arm trial to evaluate the feasibility and acceptability (attrition), and effect size of a bio-behavioral, two-component intervention to improve vulvovaginal atrophy and self-image and libido. We will also evaluate the sensitivity and effect size of the chosen outcome measures to determine the best primary outcome for a larger, well powered randomized clinical trial.

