4.2 Subject Recruitment

Recruitment and screening: Potential participants from the community will be identified in three ways: (1) physician referrals; (2) ResearchMatch.org; and (3) study advertisements including social media campaign, radio ads, flyers/brochures and a study website. Flyers may be posted in the greater Knoxville area. Locations such as churches, gyms, and cancer support groups. Brochures and flyers may be provided to physicians, providers, and organizations to distribute. IRB-approved recruitment materials may be posted on social media or in University of Tennessee/non-University of Tennessee newspapers, newsletters or websites, or read over WUOT. Participant eligibility will be determined using the Screening Eligibility Check List created from the criteria listed in 4.3.

Baseline visit: If a woman is screened eligible using the screening eligibility checklist, she will be mailed or emailed the consent form and scheduled for a virtual baseline visit. Baseline visits will be conducted using a HIPAA compliant platform (video or phone). The purpose of the baseline visit is to ensure that participants understand the study requirements, have their questions answered, be consented, complete baseline questionnaires, and are randomized. After confirming eligibility and reviewing the consent, eligible women will sign the consent using an IRB approved e-consent platform. After consent is attained, participants will be given a study number. Then baseline questionnaires will be completed, women will be randomized to vulvovaginal treatment with hypnosis starting in two weeks or vulvovaginal treatment control. Randomization will be done at the time of consent using a random number generator with “1” being the intervention group and “2” being the control group. They will then be educated about treatment with a vaginal moisturizer (see intervention details below). This treatment will begin within two weeks of completing the baseline visit (to allow for shipping of the moisturizer) and will be verified with the study coordinator. The start of vulvovaginal treatment will be confirmed by the study coordinator either through an email or phone communication with the participant. After confirmation of the start of vaginal moisturizer treatment, behavior education visit (Intervention) or follow up phone call (Control) will be planned for two weeks (+/- 3 days) for both groups.

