7.1 Analysis Plan

Aim 1: Evaluate the feasibility and acceptability of a two-component intervention for sexual function.

Feasibility will be evaluated through determining the accrual rate and screen failures. Acceptability will be determined by retention rates.

Accrual rates will be calculated by determining the number of women per month who consented to participate in the study divided by the number who were eligible and educated about the study.

For purposes of this study, screen failures will be calculated as the number of women for whom full eligibility criteria are evaluated using an eligibility checklist and initial screening call and who are determined to be ineligible through that call.

Retention will be calculated as the number of women who complete all eight weeks of the study and complete the FSFI at baseline and eight weeks divided by the number who are randomized and begin study treatment.

Conversely, attrition rates will be calculated by dividing the number of women who do not provide FSFI endpoint data for all data points by the number of women who are randomized and begin study treatment. Attrition rates of 25% or less will be considered feasible. Withdrawal reasons will be captured and reported by category.

Adherence: Adherence will be determined by calculating the number of women who begin study treatment who have at least an 80% compliance with study treatment related to the vaginal moisturizer and behavioral education materials.

This study will be determined to be feasible and acceptable if we have at least a 60% accrual rate; 80% retention rate and an 80% adherence rate (d+h under adherence).

Aim 2: Determine which measure (FSFI, ITS or PROMISE SexF) should be the primary outcome for this multi-component intervention for a larger, well powered randomized trial.

For all of the patient reported outcome measures, we will calculate missing data rates, change from baseline to each data point, and look at how variable measures are over time. This information, along with effect size data discussed in Aim 3, will be considered in determining the optimal measure to use for the primary outcome in a larger trial.

Criteria we will be looking for in a “winning” measure includes: a lack of missing data on any items; smaller “placebo” response, evidence of a better linear trend over time, and sensitivity to change.

Aim 3: Determine the effect size to be able to adequately power a larger randomized trial.

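### Section 7.1 sets two inconsistent loss limits for the primary aim (25% attrition and 80% retention), so a result that fails the study-level rule can still be reported as feasible

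*Combined protocol and SAP*

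**What the plan says.** Section 7.1 (Aim 1) holds every threshold for the primary aim.

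- **Attrition limit:** "Attrition rates of 25% or less will be considered feasible".
- **Study-level rule, shortly afterwards:** "This study will be determined to be feasible and acceptable if we have at least a 60% accrual rate; 80% retention rate", together with 80% adherence. Attrition is not among its components.
- **Role of retention:** "Acceptability will be determined by retention rates".
- **Retention numerator:** "Retention will be calculated as the number of women who complete all eight weeks of the study" and who also have the FSFI at baseline and week 8.
- **Attrition numerator:** "the number of women who do not provide FSFI endpoint data for all data points". The text introduces it as the converse of retention.
- **Denominator in 7.1:** for both rates, women who were randomized and began treatment.

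Elsewhere, the section 1.0 hypothesis is "At least 80% of randomized participants will complete the study", which counts everyone randomized. Section 4.1 gives the purpose as to "evaluate the feasibility and acceptability (attrition"), so there attrition stands for acceptability. Section 7.2 lists retention and attrition side by side in the main outcome and plans 15 women per arm.

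**The concern.** Two rates that are presented as converses over one denominator should have limits that add to 100%. Here they add to 105%. The word feasible is attached to both limits. Nothing in the plan explains the looser one, marks it as secondary or descriptive, or says which prevails.

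Feasibility and acceptability are the primary aim, and section 1.0 presents the pilot as the foundation for a grant submission for a larger trial. A borderline result could therefore be reported as feasible on attrition while failing the plan's own decision rule, with both statements traceable to section 7.1.

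Two further mismatches concern the same criterion. The numerators of retention and attrition are not exact complements, so changing 25% to 20% might not be enough. The 80% figure is also applied to different sets of women in sections 1.0 and 7.1.

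**Working it through.** **Inputs.** From section 7.1: attrition limit 25%, retention limit 80%, denominator women who were randomized and began treatment. From section 7.2: 15 per arm, so 30 if all start. The plan gives no expected retention rate and derives no sample size from these limits, so there is no plan figure to reproduce. The true retention values below are assumptions.

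**Step 1: rates as complements.** Retention of at least 80% means loss of at most 1 − 0.80 = 20%. In whole women, with 30 starters:

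- 80% retention: 0.80 × 30 = 24 retained, so at most 6 lost.
- 25% attrition: 0.25 × 30 = 7.5, so at most 7 lost.

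The verdicts split only at 7 lost: 23/30 = 76.7% retained (fails) and 7/30 = 23.3% attrition (meets 25%).

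With fewer starters:

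| Starters | Losses at which the verdicts split |
|---|---|
| 22, 23 | 5 |
| 24 | 5, 6 |
| 25, 26, 27 | 6 |
| 28, 29 | 6, 7 |
| 30 | 7 |

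**Step 2: probability of the split at 30 starters.** P(R = 23) = C(30,23) × p^23 × (1 − p)^7, where p is true retention. For p = 0.75, 0.80, 0.85 and 0.90 this is 0.166, 0.154, 0.083 and 0.018. It is also the difference between the chances of passing each limit. At p = 0.80, for example, the 25% attrition limit is met with probability 0.761 and the 80% retention limit with probability 0.607, a difference of 0.154.

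**Step 3: numerators that differ.** If completing the eight weeks means completing treatment, a woman who stops early but returns all her FSFI data is not retained, yet she is not counted as attrition. Section 5.0 (Acceptability) does group her with those who did not complete. The documents give no rate for this, so let q be the assumed share of non-retained women who return all FSFI data. Then R ~ Bin(30, p), E given R ~ Bin(30 − R, q), and attrition = (30 − R − E)/30. The split is R ≤ 23 with at most 7 counted as attrition (25% limit) or at most 6 (20% limit). At p = 0.75:

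| q (assumed) | Split, 25% limit | Split, 20% limit |
|---|---|---|
| 0% | 0.166 | 0 |
| 5% | 0.230 | 0.060 |
| 10% | 0.294 | 0.125 |
| 20% | 0.413 | 0.259 |

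At p = 0.90 the 25%-limit column runs only from 0.018 (q = 0%) to 0.024 (q = 20%). Under this reading, lowering the limit to 20% removes the split only if q is zero.

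**Step 4: denominators.** Section 4.2 randomizes women at the baseline visit and then says "This treatment will begin within two weeks of completing the baseline visit (to allow for shipping of the moisturizer"), so a woman can be randomized and never start. Illustration with assumed counts: 30 randomized, 28 start, 23 retained. On all randomized (section 1.0), 23/30 = 76.7%, below 80%. On starters (section 7.1), 23/28 = 82.1%, above 80%.

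**The case against.** The strongest reply is that the go/no-go verdict is already single. Section 7.1 has one study-level decision sentence, it omits attrition, the same section ties acceptability to retention, and section 1.0 agrees on 80%. This stands. A reader might infer that the plan contains two competing go/no-go rules, or that the probabilities above are chances of a changed study verdict. The documents do not support either. The probabilities are chances that the attrition sentence and the rule say different things.

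It can also be said that the 25% limit never binds. If the FSFI data points are baseline and week 8, every retained woman has both, so 80% retention forces attrition to 20% or less. That stands too, but it shows only that the looser limit cannot fail a study that the rule passes. The trouble is the reverse case, a failing study described as feasible.

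A reader might also infer that the mismatch can run the other way, with retained women counted as attrition because they miss an interim FSFI form. Table 2 has a row for FSFI subscales, but its marks were lost in the text available here, and the plan does not say whether such forms are endpoint data. That reading is not supported and is not relied on.

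The numerator argument depends on what completing eight weeks of the study means. A woman who stops treatment but returns the week-8 form might be read as completing the study, and the text does not settle this. The larger figures in step 3 therefore rest on one reading and an assumed q, and should be quoted only as a range.

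Finally, section 1.0 is a summary hypothesis and section 7.1 the operational definition. That makes the section 7.1 denominator the likelier one, but the plan does not say so.

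**Conclusion.** The inconsistency is real and stands in the current text, but it is modest. With 30 starters and complementary rates it affects one outcome, 23 retained and 7 lost. Its probability is between 0.018 and 0.166 across assumed true retention of 90% to 75%. With 22 to 29 starters it affects one or two counts. The 80% rule governs, and the consequence is a contradictory description of a result that fails it.

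The differing numerators could raise the chance of a split to between 0.230 and 0.413 at 75% true retention. This requires that completing the study means completing treatment and that 5% to 20% of non-retained women return all FSFI data. Neither is established by the documents.

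The denominator difference is a separate matter, and the only part that can change the 80% verdict itself. It does so only if some randomized women never start, and the plan gives no expected rate for that.

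**What to change.** 1. In section 7.1, delete the 25% threshold, or label it descriptive with no bearing on the verdict.
2. State that 80% retention alone decides this component of the study-level rule. Replacing 25% by 20% is not a sufficient substitute while the numerators can differ.
3. Report attrition as the descriptive rate of missing FSFI endpoint data, which is useful for planning the larger trial, and name the time points it covers.
4. Use one denominator for the 80% criterion in sections 1.0 and 7.1, either all randomized or randomized and began treatment, and report the other as a supporting figure.

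The cost is a few sentence-level edits and no new data. The more lenient 25% allowance is given up. If all randomized women become the denominator, those who never start will count against the 80%.

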Effect sizes, Cohen's *d* or *f*, will be calculated for from baseline to week 8. Effect sizes will be calculated for both study arms for the PROMIS, FSFI total score; FSFI lubrication, pain, and desire subscales and the Impact of Treatment Scale. Means, variance, and 95% confidence intervals will also be calculated to better estimate what sample size is needed for a larger trial with at least 80% power to detect at least a medium effect size.

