7.2 Power Considerations

Since this is a feasibility study our main outcome is to assess accrual, retention, attrition, measure sensitivity, and effect size for the multi-component intervention. A sample of 15 participants per arm will allow us to design estimates that we can use for the development of a larger study.

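### Aim 3 leaves the effect size as Cohen's d or f, uncorrected at 15 women per arm: d overstates a real effect by about 3–6%, and f is unsigned and positive even when nothing changes

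*Combined protocol and SAP*

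**What the plan says.** Section 7.1, Aim 3, states that Cohen's "d* or *f*, will be calculated for from baseline to week 8". On scope it adds: "Effect sizes will be calculated for both study arms for the PROMIS, FSFI total score", followed by three FSFI subscales and the Impact of Treatment Scale. It does not say when d applies and when f applies, which standard deviation is the divisor, whether a small-sample correction is used, or which direction counts as positive. Section 7.0 promises effect sizes for the validated measures without further detail.

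Two decisions draw on these numbers. Under Aim 2, other information on the measures, "along with effect size data discussed in Aim 3, will be considered in determining the optimal measure". Aim 3 uses them to plan the next study, whose stated target is "at least 80% power to detect at least a medium effect size"; means, variances and 95% intervals are to be reported to help size it. No numerical value is given for medium.

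The sample size comes from section 7.2: "A sample of 15 participants per arm will allow us to design estimates that we can use for the development of a larger study".

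**The concern.** At 14 or 28 degrees of freedom the choice of estimator is visible in the result. Cohen's d is inflated by a known factor that is easily removed. Cohen's f is in effect the absolute value of a t statistic on another scale, so chance variation in either direction comes out as a positive effect.

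Direction matters here. Section 5.0 says that lower FSFI scores indicate dysfunction, that the Impact of Treatment Scale measures stress, and that a higher PROMIS score means more of whatever the domain describes, with both discomfort and satisfaction among the domains. An unsigned metric compared across these scales does not show whether a measure improved or worsened, yet Aim 2 looks for sensitivity to change.

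Leaving the choice open also leaves the word medium open, because the conventional cut-offs for d and f do not describe the same within-arm change. At stake are the comparison of candidate outcomes in Aim 2 and, if the pilot estimate is carried forward, the size of the next trial.

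**Working it through.** **Inputs.** From the plan: 15 per arm (section 7.2), so 28 df between arms and 14 df for change within one arm; 80% power for the larger trial (section 7.1). Assumed, because the plan is silent: normal scores, all 15 per arm evaluable, medium meaning d = 0.5 or f = 0.25, two-sided 5% significance, f computed from partial eta-squared, and within-arm d standardized by the SD of change. The plan gives no derivation of 15 per arm, so there is no figure of its own to reproduce.

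**1. Bias of d.** The mean of d is (true d)/J, with J(df) = Γ(df/2) / [√(df/2) · Γ((df−1)/2)].

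- Between arms: J(28) = Γ(14)/[√14 · Γ(13.5)] = 0.973; 1/J = 1.028, an excess of 2.8%.
- Within arm: J(14) = Γ(7)/[√7 · Γ(6.5)] = 0.945; 1/J = 1.058, an excess of 5.8%.
- The bias is multiplicative, so at a true d of 0 the mean of d is 0.

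**2. Effect on sizing, if a between-arm d is plugged in.** A true 0.50 averages 0.50/0.973 = 0.514. A two-sample t-test at 80% power needs 64 per arm for d = 0.50 and 61 per arm for d = 0.514. With 61 per arm and a true d of 0.50, power is 78.2%. The cost is 3 women per arm and about 2 points of power.

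**3. f when nothing changes.** With one numerator df, f = √(F/df) = |t|/√df. The mean of |t| under no effect is 2√df · Γ((df+1)/2) / [√π · Γ(df/2) · (df−1)].

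| | Between arms, df 28 | Within arm, df 14 |
|---|---|---|
| Mean of \|t\| | 0.820 | 0.844 |
| Mean f = mean \|t\|/√df | 0.155 | 0.226 |
| t at f = 0.25 (0.25·√df) | 1.323 | 0.935 |
| P(f ≥ 0.25), no effect | 19.7% | 36.5% |

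By symmetry, half of these chance results are in the direction of worsening.

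**4. What f = 0.25 means in units of d.**

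- Within arm: d = t/√15 = 0.935/3.873 = 0.24, about half of the conventional medium d.
- Between arms: d = t·√(2/15) = 1.323 × 0.365 = 0.48, close to 0.5.

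The label therefore differs by metric within an arm but hardly at all between arms.

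**5. With 12 completers per arm** (the 80% retention criterion: 0.8 × 15 = 12). The inflation of d becomes 3.6% (22 df) to 7.5% (11 df). Null f averages 0.176 to 0.259 and reaches 0.25 in 25% to 42% of pilots.

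**6. Sampling error for scale.** The SE of a between-arm d of 0.5 is √(2/15 + 0.5²/60) = √0.1375 = 0.37, so an approximate 95% interval is 0.5 ± 1.96 × 0.37, or −0.2 to 1.2. The bias in step 2 is 0.014.

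**The case against.** These are exploratory aims of a feasibility pilot, and several stronger conclusions that a reader might draw do not follow.

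- *That d also makes unchanged measures look medium.* It does not do so through bias. Under no effect a |d| of 0.5 or more is sampling error, and Hedges' correction hardly changes its frequency: 18.2% to 17.0% between arms, 7.3% to 6.0% within arm.
- *That f is many times more prone than d to false medium results.* Much of that contrast comes from unequal thresholds. Within an arm, f ≥ 0.25 is the same event as |d| ≥ 0.24. Between arms, 19.7% for f compares with 18.2% for |d| ≥ 0.5. What remains is the lost sign and the mismatch of labels within an arm.
- *That the next trial will be seriously undersized.* Putting a within-arm d into a two-arm formula would give larger discrepancies, but it mixes two designs; the matched loss is 3 per arm. Even that arises only if the pilot point estimate is plugged in. The stated purpose of Aim 3 points that way, but its target of a medium effect does not require it. With a fixed d of 0.5 as the target, bias in the pilot d leaves the sample size unchanged.
- *That the correction would change which measure is chosen.* A common factor does not re-rank measures with equal df. Medium is not a threshold in Aim 2, which also weighs missing data, placebo response and linear trend. Means are reported too, so direction could be recovered.

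All of this stands and limits the size of the point. It does not justify leaving two non-equivalent metrics open, one of them unsigned, when a single corrected one costs almost nothing. That no correction will be applied is inferred from the plan's silence.

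**Conclusion.** The point holds in limited form. The plan permits two metrics that are not interchangeable, with no correction named, at a sample size where this shows. For d the overstatement of a real effect is small, and there is none at zero. For f the upward bias at no effect is substantial and direction is lost, across scales that do not all run the same way. The effect on the next trial's size is modest and conditional on plug-in use.

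The figures rest on normal data, full follow-up, f from partial eta-squared and the conventional cut-offs; attrition makes them somewhat worse. Sampling error remains the dominant uncertainty in any effect size from this pilot, and no choice of estimator removes it. The change is worth making because it gives a better estimator at almost no cost, not because the plan fails without it.

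**What to change.** In section 7.1, Aim 3, replace the choice of Cohen's d or f with one metric: Hedges' g (Cohen's d multiplied by the small-sample factor J for its degrees of freedom). Sign it so that positive means improvement on every scale, name one standardizer and use it for all measures, and report a 95% CI for g itself, since the present text does not say whether its intervals cover the effect sizes. Drop f. Use g wherever effect size enters the Aim 2 comparison, and attach any use of the word medium to a stated value of g.

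The cost is a sentence or two of analysis text and one multiplication per estimate, with no extra data, visits or participants. Reported effect sizes become about 3–6% smaller. The CI for g will be wide, and the planning of the larger trial should take that width into account.

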In summary, data demonstrates that moisturizers applied to the vagina and vulva can be helpful over time if used frequently enough. A study done by [name] et al. evaluated vaginal DHEA compared to a bioadhesive moisturizer over 12 weeks which found that daily use of a simple moisturizer improved symptoms over 12 weeks with considerable improvement demonstrated by week 4.²³ A study comparing an HLA (non-hormonal) moisturizer to Premarin cream demonstrated significant improvement in both groups by 8 weeks with no difference between the two arms.²⁹ Therefore, we will use a non-hormonal moisturizer to improve the symptoms of vulvovaginal atrophy in this study.

Libido - Energy

There is a lot of controversy in the literature about what constitutes female sexual desire, often called libido.^{30,31} It is clear that sexual desire/libido in women is multifactorial and more complex in comparison to men which appears to be more of a linear relationship between arousal and desire. In women, the relationship is not linear, and is confounded by vulvovaginal health, relationships and self-image.³² It is also likely true that sexual desire may be more challenging in women with a cancer history compared to those without cancer. Specifically, the cancer literature supports that energy (perhaps fatigue) plays an important role in sexual health and declines as a result of a cancer diagnosis and treatment.³³ Data from our recent vaginal Dehydroepiandrosterone (DHEA) study demonstrate that at baseline, vitality explained 13% of overall sexual function (unpublished data). In addition, at baseline, women in our vaginal DHEA study reported vigor/energy levels right around the 50% point (53 out of 100 with higher numbers being better) on the vitality subscale of the Medical Outcomes Scale Short Form-36. Further, linear regression modeling of overall sexual function at baseline found vitality to be a significant predictor ($p=.001$) in addition to the variables of relationship, severity and bother of vaginal symptoms, and chemically induced menopause (unpublished data).

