There are limited, yet sufficient, data to support that psychosocial interventions targeting sexual self/body image are possible and have benefit.³⁸⁻⁴³ In one study, participants were randomized to a 90 minute one-on-one session with a psychologist once a month for three months or to a wait list control to learn and practice mindfulness.³⁹ The intervention group significantly improved post treatment in every domain on the FSFI, except pain. These changes were large enough to be considered clinically important. The control group did not significantly change.³⁹ In a second study, women were randomized to six weekly 2-hour group meetings or to the control group that received printed educational materials. The intervention included education, communication training, and sex therapy. Although the groups did not differ significantly, the women who received the intervention reported greater satisfaction with sex.⁴¹

Our research team recently published a study that evaluated hypnosis versus progressive muscle relaxation for improvements in body image. The primary outcome was the breast impact of treatment scale that measures body change stress.⁴⁴ The study demonstrated that both arms improved significantly on this measure. Hypnotic techniques have a long history of being used for sexual dysfunction and ego/self-esteem strengthening.^{45,46} The objective of the suggestions is to provide women with an improved sense of well-being, health, and positive self-image. In addition, suggestions are given around increasing ones' sense of control and the ability to manage physical and mental tension that have resulted in fatigue and apathy regarding sexual activity.⁴⁵ Imagery techniques can assist women in attaining, or re-attaining, a positive view of their sexual self. We will be using our hypnotic intervention from our previously published study in this two-component trial. Suggestions for sexual desire and energy will be integrated into the hypnosis in order to address both issues within one behavioral intervention.

Summary

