Behavioral education visit: After treatment for vulvovaginal dryness has been underway for two weeks for the intervention group and VVA control group, a second remote visit will be conducted to assess how the vaginal treatment is progressing and to answer any questions about use of the moisturizer and assess for any adverse events. Also, during this second remote visit, the intervention group will be educated about the hypnotic induction intervention (see intervention information below). The rationale for splitting this education into a second visit is two-fold. First, doing it during the baseline visit would make that visit too long and too complex. It is likely participants would be overwhelmed with all of the information. Secondly, since the treatment for vulvovaginal

atrophy will take eight weeks for large effects to be seen, it is important the treatment get started and women get into that routine before adding a behavioral component. It is a standard approach in complex behavioral change to take a stepwise approach.

Phone follow up calls: Participants in both groups will have follow-up calls every two weeks (+/- 3 days) during the intervention except the week of the behavioral education visit to assess for adverse events, problem solve any lack of adherence, ensure completion of data collection and enhance study engagement.

A Screening and Enrollment Log will be maintained to document eligibility/ineligibility, screen dates, consent dates, and referral source of each individual screened.

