Perform a hypnotic induction to focus on improving body-image; suggestions for visualizing a body as strong, healthy, and beautiful. Used during study weeks 5 and 6.

Goals:

- Increase relaxation

- Build on positive feelings about your body
- Improve feelings about your sexuality
- Improve sexual experience

Audio III: Hypnotic relaxation for sexual desire and energy

Perform a hypnotic induction to improve desire for intimacy and experience increased energy and sense of wellbeing. Used during study weeks 7 and 8.

Goals:

- Increase relaxation
- Build upon improved feelings about your body
- Build upon improved feelings about your sexuality
- Improve sexual desire and energy

VVA Control

The VVA control group will get the eight weeks of vaginal moisturizer exactly as described above for the intervention group. After completion of the eight weeks of the study, the women assigned to the VVA control will be offered the Hypnotic Relaxation Intervention to complete on their own off study.

Accrual: Our research team has successfully recruited cancer survivors into clinical trials with an average of 4-6 per month. Weekly and monthly accrual goals will be set and achieved through a multipronged recruitment approach.

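### Aim 3 specifies baseline-to-week-8 effect sizes for each arm and names no between-arm contrast, although it is meant to help power a larger randomized trial and feeds the choice of primary outcome

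*Combined protocol and SAP*

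**What the plan says.** Section 1.0 states the purpose of Aim 3: "Determine the effect size to be able to adequately power a larger randomized trial". The whole method is one short paragraph at the end of 7.1. Cohen's d or f "will be calculated for from baseline to week 8. Effect sizes will be calculated for both study arms", for PROMIS, the FSFI total, three FSFI subscales (lubrication, pain, desire) and the Impact of Treatment Scale. Means, variances and 95% confidence intervals are added to help find the sample size "for a larger trial with at least 80% power to detect at least a medium effect size".

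Aim 2 in 7.1 lists the Aim 3 effect sizes among the inputs for choosing the next trial's primary outcome. The other inputs are missing data, change from baseline and variability over time. Its criteria for the preferred measure include a small placebo response.

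On the comparator, 4.4 says: "The VVA control group will get the eight weeks of vaginal moisturizer exactly as described above for the intervention group".

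**The concern.** A two-arm randomized trial is powered on a contrast between arms. Read plainly, Aim 3 gives a pre-post effect size twice, once per arm. The intervention arm's figure contains whatever the moisturizer, the passage of time and any regression to the mean contribute, as well as hypnosis. The mixing is clearest for FSFI lubrication and pain, which the moisturizer targets directly.

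Two uses are at stake. In Aim 2, a measure on which both arms improve equally can show a large within-arm d and still be a poor primary outcome for a comparison of arms. In Aim 3, if the intervention arm's pre-post d were carried into a sample size calculation and controls had also improved, the next trial would be too small.

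**Working it through.** **1. Is a between-arm contrast named anywhere?** Section 4.1 (Design) and 7.2 (Power Considerations) mention an effect size without defining it. Section 7.0 promises descriptive statistics and effect sizes. Section 7.1 gives change from baseline (Aim 2) and baseline-to-week-8 effect sizes by arm (Aim 3). None names a difference between arms, an arm-by-time term, a baseline adjustment or a standardizing SD.

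**2. Does the protocol expect controls to change?** For atrophy symptoms, yes. Section 3.0 reports that "daily use of a simple moisturizer improved symptoms over 12 weeks with considerable improvement demonstrated by week 4", and 4.2 says that treatment for vulvovaginal "atrophy will take eight weeks for large effects to be seen". For desire and body image, the evidence in 3.0 is mixed and comes from other comparators. In the team's study of hypnosis against muscle relaxation, "The study demonstrated that both arms improved significantly on this measure". In a wait-list trial measured on the FSFI, "The control group did not significantly change".

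**3. What could it cost?** The plan has no figure to reproduce: 15 per arm in 7.2 is given without a calculation, and no d, SD or correlation is stated. What follows is an illustration. Assumptions: two-sided 5% test, 80% power, equal allocation, medium effect d = 0.5, an intervention-arm pre-post d of 0.8, and both arms' d on one common baseline SD that is the same at both times, so that they can be subtracted.

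Between-arm d = intervention-arm d − control-arm d. The normal approximation is n per arm = 2(1.960 + 0.842)²/d² = 15.70/d², which gives 25, 44, 63 and 175 for d = 0.8, 0.6, 0.5 and 0.3. The two-sample t-test adds one to each:

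| Control-arm d | Between-arm d | n per arm needed | Power at 26 per arm |
|---|---|---|---|
| 0 | 0.8 | 26 | 81% |
| 0.2 | 0.6 | 45 | 56% |
| 0.3 | 0.5 | 64 | 42% |
| 0.5 | 0.3 | 176 | 19% |

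A trial sized on the pre-post d of 0.8 would have 26 per arm. If controls do not change, nothing is overstated.

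With ANCOVA on baseline, the effective d is d/√(1 − ρ²), with 2n − 3 degrees of freedom. At d = 0.5 this is 0.5/√0.75 = 0.577 for ρ = 0.5 and 0.5/√0.51 = 0.700 for ρ = 0.7. The need is then 49 or 34 per arm, and power at 26 per arm is 53% or 70%.

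**4. Does the unnamed standardizer matter?** Dividing by the SD of change instead of the baseline SD turns d into d/√(2(1 − ρ)). A change of 0.5 baseline SD becomes 0.42, 0.50 or 0.65 at ρ = 0.3, 0.5 or 0.7. Two measures with the same shift can therefore rank differently only because their baseline-to-week-8 correlations differ.

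**5. How precise would a between-arm estimate be?** Unadjusted SE = √(2/n + d²/(4n)); with ANCOVA, SE = √(2(1 − ρ²)/n + d²/(4n)). At d = 0.5, with 12 per arm taken from the 80% retention target (15 × 0.80):

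| n per arm | Method | SE | 95% CI |
|---|---|---|---|
| 15 | Unadjusted | 0.371 | −0.23 to 1.23 |
| 12 | Unadjusted | 0.415 | −0.31 to 1.31 |
| 12 | ANCOVA, ρ = 0.5 | 0.361 | −0.21 to 1.21 |
| 12 | ANCOVA, ρ = 0.7 | 0.300 | −0.09 to 1.09 |

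**The case against.** The strongest reply is that the plan does not commit the error. It reports both arms, so control change is visible beside intervention change, and an unadjusted contrast can be derived from the arm means and variances. Cohen's f could come from an arm-by-time analysis. Aim 2 already favors a small placebo response. The next trial is to be sized for at least a medium effect, so the low-power scenarios require the sponsor to set aside its own target. The aims are exploratory and the intervals wide. Finally, 7.2 wants the effect of the multi-component intervention, whereas a contrast against moisturizer isolates hypnosis.

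Much of this stands. There is no shortfall if the medium-effect target is followed, and the low-power figures are conditional. Regression to the mean is plausible but not shown, since 4.3.1 screens on yes/no symptom questions and not on a score cut-off. The comparator of the next trial is not named, so any between-arm estimate must say what it applies to.

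It does not remove the point. A contrast that could be derived is not one that is specified, and a baseline-adjusted one cannot be rebuilt from arm means and variances without the baseline-to-week-8 correlation, which Aim 3 does not ask for. The placebo criterion has no estimator, and the control arm receives an active moisturizer. Low precision limits how far any estimate can be used, but it is no reason to estimate a quantity that does not compare the arms.

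**Conclusion.** The concern holds and should be fixed. Aim 3 as written estimates within-arm change, while its stated purpose and its use in Aim 2 call for a between-arm quantity. That reading of the text is secure.

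The size of the harm is conditional. It is nil for sample size if the medium-effect target is used or if controls do not change. Under the assumed intervention-arm d of 0.8, with control-arm change of 0.2 to 0.5 SD, a trial sized on the pre-post figure would have 56% down to 19% power unadjusted. The more certain loss is in Aim 2, where measures would be compared partly on an effect size that does not reflect separation of the arms and whose standardizer is not fixed. The primary feasibility and acceptability conclusion does not depend on any of this.

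**What to change.** In 7.1, Aim 3:

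- Make the main estimate, for each listed score, the difference between arms at week 8 adjusted for the baseline score by ANCOVA and standardized by the pooled baseline SD, with its 95% confidence interval. Say which PROMIS score is meant, since 5.0 describes several domains.
- Label it the effect of hypnosis added to moisturizer, and state that it applies to a next trial with a moisturizer control. Sections 3.0 and 7.2 refer only to the two-component or multi-component intervention and leave that comparator open.
- Keep within-arm changes as descriptive, and report the SD and the baseline-to-week-8 correlation for each score.
- Keep sizing the next trial on the medium-effect target, using the pilot's SD, correlation and retention and not its point estimate.

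In 7.1, Aim 2, use the between-arm estimate as the effect-size input, and replace the placebo wording with change in the moisturizer control arm.

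The cost is a few sentences; every score needed is already planned. The drawback is that reported effects will probably be smaller and their intervals wide, so they can inform the choice of measure only loosely.
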